9.1 Missing Data

All efforts will be put forth to ensure near complete follow-up, with particular focus on the assessment of the primary outcomes and occurrence of adverse events. A reminder of subject follow-up due date will be provided to participating centres to facilitate scheduling of the follow-up visit.

In the event a subject is withdrawn prior to the six month post-activation assessment (audiometry), the analysis of the primary endpoint will involve imputing the data point captured (candidacy, activation or three months post activation) for the six month post-activation assessment. The p-value for the primary statistical endpoints will be calculated using this imputation to understand the impact of missing data on the primary results.

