8.2 Endpoints

8.2.1 Primary endpoints

The six month post-activation visit serves as the primary endpoint for data collection related to efficacy and safety outcomes post-CI532 implantation:

1. Efficacy endpoints

- 1.1. Hearing in the implanted ear will be reported as the change in pure-tone air-conduction thresholds (dB HL) pre-operatively to post-activation according to the Cochlear consensus at six months post-activation and 12 months post-activation.

Audiometric data will be summarized at each follow-up time point to assess any changes in hearing sensitivity and to characterize the impact of the procedure on hearing.

To understand if measurable low frequency thresholds can be maintained with implantation using the CI532 cochlear implant and fit with the acoustic component

- 1.2. Assessment of speech recognition in quiet will be measured using the CNC monosyllabic word test (7). Assessment of speech recognition in noise will be measured using sentences drawn from the Australian Sentence In Noise (AuSTIN) test (8) with speech-weighted noise (SWN) at a fixed +5 dB SNR.

2. Safety endpoints

- 2.1. Adverse events will be summarized by event type, severity, seriousness, as well as relatedness to the device and implant procedure will be reported and tabulated.

- 2.2. Report of medical/surgical and device related adverse events compared to the current approved labelling with regard to type, frequency and seriousness.

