8.6 Subjects

8.6.1 Inclusion Criteria

1. Meet current cochlear implant indications at the implanting centre
2. In addition to meeting current cochlear implant indications, subjects must also possess preoperative unaided hearing thresholds between 40 to 65 dB HL at 250 & 500Hz in the ear to be implanted⁴
3. Fluent⁵ speaker in the local language used to assess clinical performance

⁴ If it is more than 90 days past the date of the Candidacy Evaluation, candidacy needs to be reconfirmed by repeating hearing threshold test measures at 250 and 500Hz. Any changes observed will need to be reviewed in consultation with the Sponsor prior to surgery occurring.

4. Eighteen years of age or older at the time of implantation with no upper age limit

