8.7.2 Audiogram (Candidacy, Activation, 3 months, 6 months and 12 months post-activation)

An unaided audiogram will be performed for both ears⁸ at candidacy⁹, at initial activation, three, six and 12 months post-activation at the following pure-tone frequencies:

Air conduction: 125, 250, 500, 750, 1000, 1500, 2000, 3000, 4000, 6000 & 8000 Hz

Air conduction thresholds >80 dB HL at 125 Hz, >90 dB HL at 250 Hz, >100 dB at 8000 Hz and >120 dB for other test frequencies will be marked NR (no response).

Bone conduction: 125¹⁰, 250, 500, 750, 1000, 1500, 2000, 3000, 4000 Hz

Bone conduction thresholds >20 dB HL at 125 Hz, >30 dB HL at 250 Hz, >60 dB HL at 500 Hz and >70 dB HL for other test frequencies will be marked NR (no response).

Where the recipient reports feeling rather than hearing the acoustic stimuli, the threshold shall be recorded as vibrotactile (VT).

An aided audiogram will be performed for both ears at candidacy, and the implanted ear at initial activation¹¹, three, six and 12 months post-activation at the following frequencies using warble tones:

Aided thresholds: 125, 250, 500, 750, 1000, 1500, 2000, 3000, 4000 Hz

Tympanometry in each ear at each visit.

⁸ The use of tube phones and appropriate masking of the non-test ear is required.

⁹ If it is more than 90 days past the date of the Candidacy Evaluation, candidacy needs to be reconfirmed by repeating the air conduction hearing threshold test measure at 250 and 500Hz. Any changes observed will need to be reviewed in consultation with the Sponsor prior to surgery occurring.

¹⁰ Bone conduction measures at 125 Hz are optional based on potential audiometric equipment limitations.

¹¹ Assessing aided thresholds after the initial activation will only be conducted if there is a shift in unaided hearing of more than 10 dB HL (for the better or worse) at two or more aidable frequencies.

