8.7.2.1 Determination of hearing preservation post CI532 implantation

Unaided air conduction (AC) hearing thresholds will be reported for all participants at six months and twelve months post-activation to support the primary efficacy endpoint.

The population implanted with the CI532 device (per protocol population) will be divided into two groups for analysis:

1. Participants with a total hearing loss (no measureable AC threshold at audiometer limits at each frequency)
2. Participants with preserved hearing (measureable AC threshold at 250, 500 and 750 Hz)

Hearing preservation post CI532 implantation will be considered to be functional hearing preservation as defined by the Cochlear consensus¹²:

- i. Unaided AC hearing thresholds ≤ 70 dB HL at 250 Hz
- ii. Unaided AC hearing thresholds ≤ 90 dB HL at 500 Hz
- iii. Unaided AC hearing thresholds ≤ 90 dB HL at 750 Hz

The number of participants with a total hearing loss, preserved hearing and preserved functional hearing post CI532 implantation will be reported for each frequency (250, 500 & 750 Hz¹³).

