8.7.10 Activation (approximately 1 month post-surgery)

The CI532 cochlear implant will be activated with a commercially available Nucleus CP910 or CP920 Sound Processor and Custom Sound programming software as for recipients of existing devices. This will take place approximately 3 – 4 weeks after surgery (plus/minus 2 weeks).

Prior to activation of the sound processor, impedances and T/C levels will be determined. These data will be extracted from anonymized computer record files (“CDX”) produced by the Custom Sound software.

Initially the default ACE sound coding strategy will be used with the parameters pulse rate 900 pps per channel, 25 µs / phase, mode MP1+2, and 8 maxima. These parameters may be adjusted afterward according to local procedures to improve subjective sound quality, if deemed necessary by the clinician. The sound processor shall be programmed with the default Nucleus 6 input processing options (SCAN). Additional custom programs can be added to the sound processor in program slots 2, 3 & 4 as required.

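### Section 9.1 allows the pre-operative candidacy audiogram to stand in for the six-month result, so for a CI532 subject withdrawn between surgery and activation the missing-data check cannot show a loss at 250 or 500 Hz

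*Combined protocol and SAP*

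**What the plan says.** Section 9.1 deals with subjects withdrawn before the six-month audiogram. It says that the primary-endpoint analysis will involve "imputing the data point captured (candidacy, activation or three months post activation) for the six month post-activation assessment", and that the p-value for the primary endpoints is to be "calculated using this imputation to understand the impact of missing data on the primary results". It describes no other missing-data analysis and does not say that the captured value must be the last one or a post-operative one.

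The audiometric endpoint in section 8.2.1 is a change from before to after surgery: "Hearing in the implanted ear will be reported as the change in pure-tone air-conduction thresholds (dB HL) pre-operatively to post-activation". Section 8.7.2.1 adds counts at 250, 500 and 750 Hz of total loss, preserved hearing and functional preservation.

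Section 8.7.2 schedules audiograms at candidacy, activation and 3, 6 and 12 months, with none between surgery and activation. Section 8.7.10 places activation 3 to 4 weeks after surgery, give or take 2 weeks.

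**The concern.** The endpoint asks what implantation does to residual hearing. Section 4.2 lists complete loss of that hearing in the implanted ear as a possible result of electrode insertion. A candidacy audiogram predates insertion, so using it as the six-month result assumes that insertion did no harm.

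The rule is meant to show how far missing data could have affected the result, yet for this subject it cannot return a loss at 250 or 500 Hz. Section 8.6.4 names an adverse event as one reason for discontinuation, so leaving early need not be unrelated to outcome. What is at stake is a six-month table in which an ear never tested after surgery appears as unchanged and, at two frequencies, as preserved.

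**Working it through.** There is no figure in the plan to reproduce. Section 8.6.3 sets 12 subjects without a calculation, no dropout rate is given, and section 9 names no test for audiometry. The check is therefore a comparison of limits plus simple counts.

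**1. Who is affected.** The earliest activation is 3 − 2 = 1 week after surgery and the latest is 4 + 2 = 6 weeks. A subject withdrawn in that interval has only pre-operative audiometry. Later withdrawals have an activation or three-month audiogram.

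**2. Threshold change.** Imputed change = candidacy − candidacy = 0 dB.

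**3. Categories.** Section 8.6.1 requires "preoperative unaided hearing thresholds between 40 to 65 dB HL at 250 & 500Hz in the ear to be implanted". The first functional limit in section 8.7.2.1 is "Unaided AC hearing thresholds ≤ 70 dB HL at 250 Hz"; the limits at 500 and 750 Hz are both 90 dB HL. Section 8.7.2 sets the no-response limits: ">90 dB HL at 250 Hz, >100 dB at 8000 Hz and >120 dB for other test frequencies will be marked NR".

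| Frequency | Entry range (dB HL) | Functional limit (dB HL) | Margin (dB) | No response above (dB) |
|---|---|---|---|---|
| 250 Hz | 40 to 65 | 70 | 5 to 30 | 90 |
| 500 Hz | 40 to 65 | 90 | 25 to 50 | 120 |
| 750 Hz | none set | 90 | not fixed | 120 |

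In 5 dB steps there are 6 × 6 = 36 eligible pairs of thresholds at 250 and 500 Hz. All 36 are measurable and within the functional limits at both frequencies. The total-loss group is defined as "Participants with a total hearing loss (no measureable AC threshold at audiometer limits at each frequency"; a measurable value at 250 or 500 Hz rules it out. Nothing follows for 750 Hz, where entry sets no limit, and so nothing follows for a classification that needs all three frequencies.

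**4. Loss that would be hidden on the dB scale.** Suppose the true six-month result were no response. The loss would exceed 90 − 65 = 25 to 90 − 40 = 50 dB at 250 Hz, and 120 − 65 = 55 to 120 − 40 = 80 dB at 500 Hz. One such subject in 12 moves the mean change by more than 25/12 = 2.1 to 50/12 = 4.2 dB at 250 Hz, and by more than 55/12 = 4.6 to 80/12 = 6.7 dB at 500 Hz.

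**5. Effect on a proportion at 250 or 500 Hz.** Assume one affected subject in 12, and assume that imputed values enter the counts. With x of the other 11 preserved, the rule reports (x + 1)/12 and the worst case is x/12. The gap is 1/12 = 8.3 points.

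| Observed | Rule (best case) | Worst case |
|---|---|---|
| 3/11 = 27.3% | 4/12 = 33.3% | 3/12 = 25.0% |
| 6/11 = 54.5% | 7/12 = 58.3% | 6/12 = 50.0% |
| 9/11 = 81.8% | 10/12 = 83.3% | 9/12 = 75.0% |

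If q is the chance that this subject's hearing was lost, the expected overstatement is q/12: 0.8 points for q = 10%, 2.5 for 30% and 4.2 for 50%. These values of q are assumptions. For comparison, the exact 95% confidence interval for 6/11 is 23.4 to 83.3%.

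**6. Whether another rule removes the subject.** Replacement in section 8.6.5 covers pre-operative withdrawal only. The top-up in section 9 depends on the completed-cases population, which section 9 defines by CI532 implantation, so on that definition this subject still counts towards 12. Section 8.7.2.1 also defines the per-protocol population by implantation. Section 22.2, however, restricts per-protocol analysis to subjects who completed treatment with a full dataset, which would leave this subject out.

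**The case against.** The strongest reply is that the subject may not be in the primary analysis at all. That analysis is per protocol, and the section 22.2 definition would exclude anyone lost before activation. This stands as an unreconciled conflict and lowers certainty. It does not remove the defect: the same definition would exclude every subject for whom section 9.1 imputes, which would leave section 9.1 with nothing to do.

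Second, section 9.1 names only the primary-endpoint analysis and its p-value. It does not say that imputed values feed the section 8.7.2.1 counts, which describe hearing after implantation. This is correct, so the percentages above are conditional. The 0 dB change is not.

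Third, a reader might infer that the rule always gives the most favourable result. The documents do not support that. At 750 Hz the outcome depends on the candidacy value. On the scale of improvement, no change and decrement in section 9, 0 dB falls under no change, which is not the best category. A retest more than 90 days after candidacy could also show a shift for review with the sponsor (section 8.6.1); the documents do not say whether a subject then above 65 dB HL could proceed.

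Fourth, the practical harm is small. The window is short, section 5.2 states no formal hypothesis, and section 9 sets no pass/fail criteria. The by-visit summaries and individual data would probably reveal the missing post-operative audiogram. This stands and sets the severity.

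**Conclusion.** The rule is wrong as written, but the fix is minor. For a CI532 subject lost between surgery and activation, a pre-insertion value becomes the six-month result, with a change of 0 dB whatever happened to the ear. If imputed values enter the counts, and barring a shift on retest, that subject is functionally preserved at 250 and 500 Hz and cannot be a total loss. With one affected subject in 12, which is an assumption, a proportion at either frequency is too high by 8.3 points if hearing was lost and by 0 if it was not. That is small beside the sampling uncertainty.

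Two wider conclusions are tempting and unsupported. One is that all imputation under section 9.1 hides surgical loss: activation and three-month audiograms are post-operative and can show it. The other is that the study's main result is biased: the documents do not show that any subject will fall in this window. Section 3 reports that most subjects lost residual hearing with version 1 of the assembly, but the sheath has since been redesigned, so that is no estimate for this device.

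**What to change.** In section 9.1:

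1. Delete candidacy as a source for imputing post-operative audiometry.
2. State that the last post-operative audiogram, from activation or three months, is the one carried forward, and label the imputed analysis as sensitivity. The label matters because hearing may still change after that audiogram.
3. For CI532 subjects with no post-operative audiogram, report observed cases together with best-case and worst-case counts at each frequency.
4. Reconcile the per-protocol definition in section 22.2 with sections 8.7.2.1, 9 and 9.1, so that it is clear whether withdrawn subjects belong to the primary analysis.

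The cost is a few sentences, plus one small table that is needed only if such a subject occurs. No new data are required. The downside is a possibly less favourable or wider figure in that case.

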9 STATISTICAL CONSIDERATIONS

All subjects who are recruited to the clinical investigation will constitute the intention-to-treat (ITT) population for the purposes of safety evaluation. Only subjects implanted with the CI532 will be considered as the completed cases (CC) population and per protocol (PP) analysis of the primary endpoint will be performed.

Where the CC population is insufficient, the sponsor reserves the right to ask the centres to recruit additional cases in order to reach the desired sample size of 12. As this is a feasibility clinical investigation, there have been no formal power or sample size estimations performed for the primary objectives.

To understand if measurable low frequency thresholds can be maintained with implantation using the CI532 cochlear implant and fit with the acoustic component:

1. Audiometric data will be summarized at each follow-up time point to assess any changes in hearing sensitivity and to characterize the impact of the procedure on residual hearing.
2. The degree of hearing will be reported and tabulated as the number of subjects who have measurable residual hearing post CI532 implantation.

The number, severity and relationship of adverse events will be reported and tabulated. The rate of device-related adverse events will be compared to known rates of device-related adverse events for the commercially approved Nucleus cochlear implants.

Pre- to post-operative gains in speech and SSQ scores will be tested using paired comparisons (Student's t or non-parametric test if more appropriate). GBI scores will be compared to a hypothesised mean score of 0 (no benefit).

There are no pass/fail criteria to be applied to the results of the clinical investigation.

If required an interim analysis and report on three month speech and hearing threshold data will be provided for the purposes of submission to the TGA.

The characteristics of the study group will be presented descriptively. Quantitative variables such as age will be presented with mean, standard deviation, median, minimum and maximum and 95% CI. Qualitative variables such as age or gender will be presented as percentages and observed frequencies. If differences in outcome are found for subgroups defined by baseline age or gender, analyses will be performed to explore the possible role of other baseline characteristics to explain the results.

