Supportive efficacy analyses will include analysis of individual data for all measures to establish the proportions of those subjects showing improvement, no change, and decrement in performance on the primary audiometry endpoint.

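### Section 9.1 lets a pre-surgery audiogram stand in for a missing six-month audiogram; for a subject withdrawn before activation it is the only scheduled value and passes the 250 and 500 Hz limits by inclusion

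*Combined protocol and SAP*

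**What the plan says.** - **Imputation (9.1).** For a subject withdrawn before the six-month audiometry, the primary endpoint analysis will involve "imputing the data point captured (candidacy, activation or three months post activation) for the six month post-activation assessment". The section does not say which value applies when several exist, and it does not restrict the source to post-operative tests. It adds that a p-value will be calculated "using this imputation to understand the impact of missing data on the primary results".
- **Schedule (8.7.2, 8.7.10).** Unaided audiograms are taken at candidacy and then "at initial activation, three, six and 12 months post-activation at the following pure-tone frequencies". None is scheduled at surgery or between surgery and activation. Activation is planned about 3 to 4 weeks after the operation, with a tolerance of 2 weeks either way.
- **Eligibility (8.6.1).** The ear to be implanted must have "preoperative unaided hearing thresholds between 40 to 65 dB HL at 250 & 500Hz". Nothing is required at 750 Hz.
- **Functional preservation (8.7.2.1).** The limits are "Unaided AC hearing thresholds ≤ 70 dB HL at 250 Hz", and 90 dB HL at both 500 and 750 Hz. Counts are reported for each frequency.
- **Population (9).** "Only subjects implanted with the CI532 will be considered as the completed cases (CC) population", and the primary endpoint is analysed per protocol. Automatic replacement under 8.6.5 covers pre-operative withdrawal only.
- **Individual analysis (9).** Supportive analyses give the "proportions of those subjects showing improvement, no change, and decrement in performance on the primary audiometry endpoint".

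**The concern.** The audiometric question is what happens to residual hearing after the electrode is inserted. Section 4.2 warns that insertion can abolish it, and Section 3 reports that most subjects in the early feasibility trial of the first version of the array lost theirs. A test done before surgery cannot speak to that question. If it is carried into the six-month cell, the subject's status at 250 and 500 Hz is settled by the eligibility criteria rather than by the outcome. A subject whose hearing was lost at surgery could then be counted as within the functional limits at both frequencies, and as unchanged in the individual analysis.

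Preservation counts and threshold change make up the audiometric part of the primary efficacy report, and Section 3 says the results may support a later randomised trial. Section 9.1 does not ask for imputed values to be marked, so a reader of the table could not see that this had happened.

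**Working it through.** The plan gives no figure to reproduce: 12 is a fixed feasibility number with no power calculation (8.6.3). The check compares the rules with one another and then sizes the effect.

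**1. When candidacy is the only value.** From 8.7.10, activation falls between 3 − 2 = 1 week and 4 + 2 = 6 weeks after surgery. A subject withdrawn after implantation but before activation has no scheduled post-operative audiogram. The repeat test required when candidacy is more than 90 days old (footnotes to 8.6.1 and 8.7.2) is also pre-surgery.

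**2. Whether that value can fail the limits.** Margin = functional limit − candidacy threshold.

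| Frequency | Limit (dB HL) | Candidacy range (dB HL) | Margin, worst eligible ear | Margin, best eligible ear |
|---|---|---|---|---|
| 250 Hz | 70 | 40 to 65 | 70 − 65 = 5 dB | 70 − 40 = 30 dB |
| 500 Hz | 90 | 40 to 65 | 90 − 65 = 25 dB | 90 − 40 = 50 dB |
| 750 Hz | 90 | not set by inclusion | not determined | not determined |

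Every eligible candidacy value passes at 250 and 500 Hz. The imputed change is candidacy minus candidacy, or 0 dB.

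**3. Effect on a per-frequency count.** Assume 12 implanted subjects, 1 withdrawn before activation, and 8 of the other 11 within the limit at one given frequency (250 or 500 Hz). The intervals are exact (Clopper-Pearson): the lower limit is the 2.5% quantile of Beta(x, n − x + 1) and the upper limit is the 97.5% quantile of Beta(x + 1, n − x).

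| Handling of the withdrawn subject | Count | Proportion | 95% CI |
|---|---|---|---|
| Candidacy carried | 9/12 | 75.0% | 42.8 to 94.5 |
| Reported as missing | 8/11 | 72.7% | 39.0 to 94.0 |
| Counted as not preserved | 8/12 | 66.7% | 34.9 to 90.1 |

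Carried against not preserved: 9/12 − 8/12 = 1/12 = 8.3 points. This is the most one subject can move the count, whatever the other 11 show. Missing against not preserved: 72.73 − 66.67 = 6.06, about 6.1 points, so simply leaving the subject out can also flatter the proportion. If hearing was in fact kept within the limit, the carried count is right.

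**4. Effect on mean change.** A 0 dB entry dilutes the mean. If the other 11 had an assumed mean loss of 20 dB, the mean over 12 would be 20 × 11/12 = 18.3 dB.

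**5. How often.** The documents give no rate for withdrawal in this window. For an assumed per-subject probability p, the chance of at least one case in 12 is 1 − (1 − p)^12. This gives 3.0% at p = 0.25%, 5.8% at p = 0.5% and 11.4% at p = 1%. Only some of these subjects would have lost hearing and so be miscounted.

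**The case against.** The strongest reply is that 9.1 describes a sensitivity analysis. Its only stated output is a p-value meant to show the impact of missing data. Section 9 names tests for speech, SSQ and GBI but none for audiometry, and 5.2 says there is no formal hypothesis. The audiometric report is a tabulation of hearing after implantation, and a pre-surgery test does not naturally belong in it. This stands in part: a reader might infer that the carried value certainly enters the main preservation table, and the text does not establish that. But the reply does not rescue the rule. The same section says that the primary endpoint analysis will involve the imputation, and it gives no other handling. As a sensitivity analysis the rule is uninformative for this subject, because at 250 and 500 Hz it can return only the favourable answer.

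A second reply is that the subject would drop out anyway, because 22.2 describes per-protocol analysis in terms of a complete dataset. Section 9, however, defines the analysed group by implantation with the CI532, so the subject's place is at best unsettled.

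A third reply is about size: the case is rare, one subject moves a count by 8.3 points against intervals more than 50 points wide, and the withdrawal reason is recorded, so in 12 subjects at one site the case would be identifiable. This stands and limits the point to a minor correction.

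Three stronger readings are not supported:

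- **Full functional preservation is guaranteed.** It is not, because inclusion does not bound 750 Hz.
- **The understatement of mean loss can be fixed in decibels by assuming total loss.** The plan sets no numeric value for no response, and a footnote to 8.7.2.1 allows the median.
- **The withdrawal rules in 8.6.4 and 19 must be rewritten so that audiograms continue after explant.** That is a separate matter. It is partly covered by 17.2 (follow-up after incidents), 8.6.4 (subjects given an alternative device stay in) and the commitment in 9.1 to near-complete follow-up.

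**Conclusion.** The concern holds as a minor correction. Section 9.1 expressly permits a pre-surgery audiogram as the six-month value. For a CI532 subject withdrawn between surgery and activation it is the only scheduled value. It must pass at 250 and 500 Hz, it shows no change, and it errs in the device's favour if hearing was lost. This is a stated rule that can give a wrong entry, not a missing detail.

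The size is at most 1 of 12 per frequency for each such subject. It arises only if three things coincide: withdrawal in the window of about 1 to 6 weeks, hearing at that frequency actually worse than the limit, and the carried value being used in the reported count. The first has no rate in the documents; the range above is an assumption. A reader might infer that the study's conclusion is at risk. With no hypothesis, no pass/fail criterion, and individual data analysed, the documents do not support that.

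**What to change.** In Section 9.1:

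1. Delete candidacy as an imputation source.
2. Carry forward only the latest post-operative unaided audiogram (activation or three months), and flag it as imputed wherever it appears.
3. Report implanted subjects with no post-operative audiogram as missing in the main table, and add one bounding line that counts them as not preserved.
4. State that the imputed analysis is a sensitivity analysis of the preservation counts, in place of the reference to a p-value for which no audiometric test is defined.

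The cost is a short amendment and one extra table line, with no new visits or tests. The downside for the sponsor is a possibly slightly less favourable figure if such a subject occurs.

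### Section 9.1 attaches its imputation and p-value to six-month audiometry, which has no named test, and gives no withdrawal rule for speech gain, the primary endpoint that is tested

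*Combined protocol and SAP*

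**What the plan says.** Section 9.1 sets the withdrawal rule: "In the event a subject is withdrawn prior to the six month post-activation assessment (audiometry), the analysis of the primary endpoint will involve imputing" a value taken from an earlier visit. The full source list is "imputing the data point captured (candidacy, activation or three months post activation) for the six month post-activation assessment". The next sentence states the purpose: "The p-value for the primary statistical endpoints will be calculated using this imputation to understand the impact of missing data on the primary results".

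Section 9 describes the analyses. For hearing, "Audiometric data will be summarized at each follow-up time point to assess any changes in hearing sensitivity", together with a count of subjects with measurable residual hearing. A supportive analysis gives the proportions who are better, the same or worse. For speech, "Pre- to post-operative gains in speech and SSQ scores will be tested using paired comparisons", by Student's t or a non-parametric test.

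Section 8.2.1 makes the six-month visit the primary time point and lists speech as efficacy endpoint 1.2: "Assessment of speech recognition in quiet will be measured using the CNC monosyllabic word test", with AuSTIN sentences for noise. The synopsis also lists clinical performance in quiet and noise as a primary endpoint.

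**The concern.** The imputation rule and the significance test belong to different primary endpoints. Section 9.1 promises an imputed p-value, but the endpoint that is imputed has no test to produce one, and the endpoint that is tested has no imputation.

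Speech gain matters here. Section 6 lists the pre-to-post speech benefit as a performance claim to be verified, and section 3 says the results may support a later randomised trial. With 12 subjects, each missing six-month score has visible weight. The check in section 9.1 is the only one the plan offers on the effect of missing data, and followed as written it does not reach the tested endpoint.

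**Working it through.** The documents give no alpha, power, effect size, SD or dropout rate, and the 12 subjects are stated without derivation. There is no planned figure to reproduce, so the check is first textual and then illustrative.

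**Step 1. Match each primary endpoint to its analysis and its withdrawal rule.**

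| Primary endpoint (8.2.1) | Analysis in section 9 | Rule in 9.1 |
|---|---|---|
| Audiometry (1.1) | Summaries, counts, proportions; no test named | Imputed from an earlier visit |
| Speech in quiet and noise (1.2) | Paired t or non-parametric test | None |
| Safety (2.1, 2.2) | Tabulation, comparison with known rates; no test named | None |

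No row has both a named test and an imputation rule. SSQ and GBI are also tested, but they are secondary.

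**Step 2. Check whether the rule could be meant for speech.** The permitted sources are candidacy, activation and three months. Audiograms are taken at all three (section 8.7.2, Table 1). Speech is measured at candidacy and at 3, 6 and 12 months, not at activation (section 8.7.3, Table 1). The source list follows the audiogram schedule.

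**Step 3. Effect on mean speech gain.** Assume k of 12 implanted subjects withdraw before six months with a true gain of zero, and the others have mean gain M. The all-subject mean is M(12 − k)/12, so the observed mean overstates it by 12/(12 − k) − 1:
- k = 1: 12/11 − 1 = 9%
- k = 2: 12/10 − 1 = 20%
- k = 3: 12/9 − 1 = 33%

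Seen from the other side, carrying the candidacy score forward lowers the mean by k/12: 8.3%, 16.7% or 25%.

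**Step 4. Effect on the test.** Illustration with assumed values: 10 observed pairs, mean gain 30 points, SD 20.
- Observed pairs: t = 30/(20/√10) = 4.74, p = 0.0011.
- With two zero gains added: mean = 300/12 = 25; variance = (9 × 400 + 10 × 900 − 12 × 625)/11 = 463.6; SD = 21.5; t = 25/(21.5/√12) = 4.02, p = 0.0020.

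Two-sided p-values over a range of assumed standardised gains (mean/SD among observed pairs), observed pairs against candidacy carried forward:

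| Gain/SD | 1 withdrawn | 2 withdrawn | 3 withdrawn |
|---|---|---|---|
| 0.5 | 0.128 / 0.128 | 0.148 / 0.147 | 0.172 / 0.169 |
| 0.8 | 0.024 / 0.025 | 0.032 / 0.034 | 0.043 / 0.046 |
| 1.0 | 0.008 / 0.009 | 0.012 / 0.014 | 0.017 / 0.021 |
| 1.5 | 0.0006 / 0.0008 | 0.0011 / 0.0020 | 0.0020 / 0.0043 |

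The mean gain moves far more than the p-value.

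**Step 5. What the rule does to audiometry.** Eligibility requires 40 to 65 dB HL at 250 and 500 Hz (section 8.6.1). The functional-preservation limits are 70 dB HL at 250 Hz and 90 dB HL at 500 Hz (section 8.7.2.1). Since 65 is below both limits, a carried-forward candidacy audiogram always counts as preserved at those two frequencies. Example at one frequency, assuming two withdrawals and 6 of 10 observed subjects preserved (60.0%): with candidacy imputed, 8/12 = 66.7%; with the two counted as not preserved, 6/12 = 50.0%. Eligibility sets no limit at 750 Hz, so this does not extend there.

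**The case against.** The best defence is that section 8.2.1 uses the term primary endpoint for the whole six-month visit, which includes speech. On that reading the word in brackets in 9.1 only labels the visit, the plural in the p-value sentence covers speech in quiet and noise, and speech can be filled from candidacy or three months. This is possible, but the audiometry label and the activation source fit it poorly. If it was intended, 9.1 still needs to say so.

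Four stronger readings are tempting, and the documents do not support them.
- *The check is impossible.* Endpoint 1.1 is a change in dB thresholds, so a paired p-value could be computed. The test is unnamed, not unavailable.
- *The plan restricts speech to completers.* Sections 9 and 8.7.2.1 define the efficacy set by receipt of the CI532. The general per-protocol definition in section 22.2 mentions a complete dataset, but it is written for allocated treatment groups. Section 9 also ties the speech test to no single visit, so someone leaving after three months could still give a three-month pair. Dropping out of the six-month comparison is a consequence of having no rule, not a stated exclusion.
- *Withdrawn subjects are those with poor benefit.* Sections 8.6.4 and 19 list device failure, explant and adverse events, but also loss to follow-up and personal decision. Subjects given an alternative device stay in the study. Poor benefit is an assumption.
- *The conclusion on speech would change.* The p-values in the illustration hardly differ.

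It also stands that sections 5.2 and 9 set no formal hypothesis and no pass/fail criterion, and that individual outcomes will be reported, so missing scores among 12 subjects should be visible.

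**Conclusion.** The concern holds as a mismatch. Section 9.1 ties its imputation to an endpoint without a named test and leaves the tested primary endpoint without a withdrawal rule, so the promised missing-data check is not defined as written. A CI532-implanted subject with no six-month speech score leaves the six-month paired comparison with nothing to show the effect.

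The possible overstatement of mean speech gain is 9%, 20% or 33% for 1, 2 or 3 withdrawals of 12. This rests on zero gain in withdrawn subjects and on assumed withdrawal numbers. The effect on significance is slight, and no study decision depends on it. The matter is worth correcting because the plan itself commits to the check and treats speech benefit as a claim to verify; it does not undermine the study.

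**What to change.** In section 9.1:

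1. For CNC in quiet and AuSTIN in noise, report the six-month paired comparison (mean gain, 95% CI and p-value) in observed pairs. As a sensitivity analysis, repeat it in all CI532-implanted subjects with the candidacy score carried forward, that is, a gain of zero, for those without a six-month score. Add a version that uses the three-month score where it exists. Zero gain is a deliberately cautious choice, not an estimate, and should be labelled so.
2. For audiometry, replace the p-value sentence with descriptive results with and without imputed values. Removing the p-value alone would leave unseen that a carried-forward candidacy audiogram counts as preserved at 250 and 500 Hz.

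The cost is a few sentences and one or two extra table rows. No new data are needed, since candidacy and three-month speech scores are already scheduled in Table 1. The sensitivity estimate may be less favourable than the main one.
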